## 9.7 Safety Analyses

The safety analysis will utilize the Safety Analysis Set.

### 9.7.1 Adverse Events

Adverse events will be mapped to system organ classes and preferred terms using the MedDRA dictionary version 20.1. All adverse event summaries will be restricted to treatment emergent adverse events (TEAE), which are defined as those AEs occurring on or after dosing and those

existing AEs worsening during the study. Only treatment-emergent adverse events will be included in the summary tables.

For all AE tables, counting will be by subject and not by event. In other words, if a subject has more than one event with the same preferred term, the subject will be counted once for that preferred term in the treatment group. If a subject has more than one event in the same system organ class, the subject will be counted once for that system organ class in the treatment group.

An overall summary of AEs will be presented. The overall summary will include the number and percentage of subjects experiencing any AEs, study drug related AEs, AEs by maximum severity (highest toxicity grade), SAEs, study drug related SAEs, discontinued due to AE, and deaths. The number and percentage of subjects experiencing each AE, study drug related AE, and SAEs will be summarized by treatment group according to system organ class and preferred term. Additional table including only preferred term summarized by treatment for the number and percentage of subjects experiencing each AE will be presented as well.

Complete subject listings of all AE will be provided. For each AE the following will be specified: treatment group, start and stop dates, severity grade, MedDRA system organ class and preferred term, duration, relationship to study treatment, action taken, outcome of the adverse event and seriousness.

#### **Partial or Missing AE Start and Stop Dates**

If the AE start date is incomplete, then it will be imputed as follows for the purpose of determining the onset of AE only:

In the event that the day portion (and only the day portion) of the AE onset date is missing:

- If the start date is completely missing, the start date will be equal to the first dose date. However, if the stop date is not missing and is before the first dose date, then the stop date will be used instead.
- If the start day is missing, the day of the first dose date will be used for the event occurring at the same month and year of the first dose date; otherwise, the first day of the month will be used.
- If the start day and month are missing, then the first day of the first month (January) will be used.

If the AE stop date is partial, then it will be imputed as follows for the purpose of determining the duration of AE only:

- If the stop date is completely missing and the event is not ongoing, the stop date will be equal to the last dose date or date of completion/withdrawal, whichever is the latest.
- If the stop day is missing, the day of the last study day will be used for the event stopping at the same month and year of the last study day; otherwise, the last day of the month will be used.
- If the stop day and month are missing, then the last day of the last month (December) will be used.

The aforementioned missing or partial data handling rules will be applied to the summary tables. The recorded missing or partial date values will be presented in the listings.

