7.2 Methods and Timing for Recording and Reporting Adverse Events

7.2.1 Adverse Event Reporting Period

Any AE occurrence during the study must be recorded on source documentation and eCRF at the site, in accordance with protocol instructions.

AEs and SAEs will be recorded from the first study drug administration through the follow-up visit. After the 4-week follow-up visit, only SAEs that are believed to be drug-related should be reported.

After informed consent but prior to initiation of study drug, only SAEs considered by the investigator to be caused by a protocol-mandated intervention will be collected (e.g. SAEs related to invasive procedures such as blood collection). These procedure-related SAEs should only be reported on the SAE form, not on the AE form of the eCRF. Subjects who undergo screening procedures but are not randomized into the study will not have SAEs recorded in the clinical database.

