## 8.3 Handling of Missing Data and Excluded Therapy Use

For summary statistics results will generally be reported based upon observed data. Should a determination of treatment period (on treatment, pre-treatment) be required for AEs or concomitant medication but the corresponding date is missing, or is a partial date, the event/medication will be considered on treatment unless the portions of the date that are available indicate this is not possible.

In case of missing data for the 24-hr cough frequency and the awake cough frequency, two selected imputation approaches are specified for the sensitivity analyses (Section 9.6.5).

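### An adverse event dated only to the year of first dose is imputed to 1 January and so leaves the TEAE tables, contrary to SAP 8.3 and protocol 8.2

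*SAP*

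**What the plan says.** The AE start-date rules are in SAP 9.7.1, under the heading on partial or missing AE dates. There are three cases:

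- **Date completely missing:** the first-dose date is used, or the stop date if that is known and falls before first dose.
- **Day missing:** "the day of the first dose date will be used for the event occurring at the same month and year" as first dose; in any other month, the first of the month.
- **Day and month missing:** "If the start day and month are missing, then the first day of the first month (January) will be used".

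The section then states: "The aforementioned missing or partial data handling rules will be applied to the summary tables".

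Earlier in 9.7.1, a treatment-emergent event is defined as one with onset at or after dosing, or an existing event that worsens. The SAP adds: "Only treatment-emergent adverse events will be included in the summary tables".

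The general missing-data rule in SAP 8.3, worded identically in protocol 8.2, covers an AE or medication that must be classed as pre-treatment or on treatment when its date is missing or partial: "the event/medication will be considered on treatment unless the portions of the date that are available indicate this is not possible".

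On collection, protocol 7.2.1 says: "AEs and SAEs will be recorded from the first study drug administration through the follow-up visit".

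**The concern.** The two rules classify the same record in opposite ways. A known year equal to the year of first dose is compatible with onset on treatment, so SAP 8.3 counts the event. SAP 9.7.1 moves it to 1 January, before first dose for almost everyone, and so excludes it.

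The result is also odd within 9.7.1. An event with no date at all is counted as treatment-emergent, while one with a known and compatible year is not.

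The events at risk are ones the trial means to count. AEs are recorded only from first dose. Under protocol 7.2.1, procedure-related SAEs before dosing go on the SAE form and not on the AE page. Under protocol 7.1.3, clinically significant findings before dosing go to medical history. A year-only record on the AE page should therefore be a post-dose event.

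The tables affected include the overall AE summary, drug-related AEs, SAEs, discontinuations due to AEs, and deaths. The imputation can only remove events from these tables. With 85 subjects per arm, one lost event changes an incidence by 1/85, about 1.2 percentage points.

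**Working it through.** The plan gives no figure on this point, so there is none to reproduce. The check sets the rules side by side and then counts cases.

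**Step 1. Classify one event under each rule.** Take an AE with only the year recorded, equal to the year of first dose, and no stop date before first dose.

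| Rule | Onset or status assigned | In the TEAE tables? |
|---|---|---|
| SAP 9.7.1, day and month missing | 1 January | No, unless first dose was on 1 January or a worsening is recorded |
| SAP 8.3 and protocol 8.2 | On treatment, since the year does not rule it out | Yes |

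Two records with different gaps show how the neighbouring 9.7.1 rules behave:

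| Record | Onset assigned by 9.7.1 | In the TEAE tables? |
|---|---|---|
| Start date completely missing | First-dose date | Yes |
| Day missing, month of first dose | Day of first dose | Yes |

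**Step 2. Count how often 9.7.1 excludes a post-dose event.** Inputs:

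- Study Day 1 is the date of first dose (SAP 7.2).
- Treatment lasts 84 days, and the last scheduled visit is Day 113 (protocol 3.1 and 6.5.11).
- Assumption: first dose is equally likely on each day of a 365-day year, and onset on each Study Day. The documents give neither enrolment dates nor AE timing.

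An event is excluded when its true onset falls in the calendar year of first dose and first dose is not on 1 January. For first dose on day *d* of the year and onsets on Study Days 1 to *L*, the number of onsets in the same year is min(*L*, 366 − *d*).

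For *L* = 113:

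- All combinations: 365 × 113 = 41,245.
- Onset in the first-dose year: 253 × 113 + (112 × 113)/2 = 28,589 + 6,328 = 34,917.
- Less first dose on 1 January: 34,917 − 113 = 34,804.
- Excluded: 34,804/41,245 = 84%.

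For *L* = 84:

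- All combinations: 365 × 84 = 30,660.
- Excluded: 282 × 84 + (83 × 84)/2 − 84 = 27,090.
- Share: 27,090/30,660 = 88%.

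Among events in the first-dose year alone, the share for *L* = 113 is 34,804/34,917 = 99.7%.

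**Step 3. Vary the first-dose date** (15th of the month, onset on Days 1 to 113):

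| First dose | Excluded by 9.7.1 |
|---|---|
| January to August | 100% |
| September | 108/113 = 96% |
| October | 78/113 = 69% |
| November | 47/113 = 42% |
| December | 17/113 = 15% |

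The share falls late in the year because more onsets then belong to the next calendar year, and 1 January of that year is after first dose.

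**Step 4. Apply the alternatives.** Under SAP 8.3, none of these events is classed as pre-treatment. The same holds if 9.7.1 uses the first-dose date for an event in the first-dose year and 1 January otherwise: 0% excluded.

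**Where the rule may have come from.** The year-only sentence is identical to the one for medications in SAP 9.4. It does little harm there, because a medication is concomitant if either its start or its stop is on or after first dose, and a year-only stop date goes to the end of December. AE status turns on onset. The day-missing rule differs between the two sections in allowing for the month of first dose; the year-only rule has no such allowance.

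**The case against.** The best reply is that SAP 8.3 already governs. It addresses the pre-treatment or on-treatment classification directly, whereas 9.7.1 says its start-date imputation serves only to fix onset. The lead-in to the 9.7.1 rules also limits them to dates missing just the day, which read literally leaves out the year-only case. This does not settle the matter. Treatment-emergent status is defined by onset, 9.7.1 applies its dates to the summary tables, and the SAP states no precedence. The lead-in fits the completely-missing rule no better. A programmer following the year-only rule as written would exclude the event.

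Several limits do stand:

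- Events dated in a later calendar year remain treatment-emergent.
- A recorded worsening could bring an event back into the tables.
- The AE listings are complete and show the partial date, so the event leaves the tables but not the report.
- Year-only dates should be rare. AEs are sought at every contact, scheduled contacts are at most 28 days apart (visit windows aside), and monitors review every eCRF. SAEs must be notified, and drug discontinuations communicated to the sponsor, within 24 hours, so these are among the least likely to lack a month.
- The rule is the same in both arms of a blinded trial. The bias shown is in the counts, not in the comparison between arms.

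**Conclusion.** The concern holds. For a year-only AE in the year of first dose, SAP 9.7.1 contradicts SAP 8.3, protocol 8.2 and the logic of its own two neighbouring rules, and it errs toward under-counting. Given such a record, exclusion is close to certain: it is avoided only by a first dose on 1 January or a recorded worsening. Across all post-dose year-only events the excluded share is 84% (Days 1 to 113) or 88% (Days 1 to 84), leaving worsening aside. These two figures rest on the assumed even spread of dates and are conditional on a year-only record existing. The number of such records is not in the documents and is probably small, so the practical impact is low. The correction should still be made before database lock, because the classification would otherwise depend on which section the programmer follows.

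**What to change.** Replace the year-only start-date rule in SAP 9.7.1 with: if day and month are missing and the year is that of first dose, use the first-dose date, unless a known stop date precedes first dose, in which case use the stop date; for any other year, use 1 January. This brings the rule into line with SAP 8.3, protocol 8.2 and the completely-missing rule, and leaves events from earlier or later years correctly classed.

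In the same edit, correct the lead-in so that it covers all three kinds of missing date, and state that SAP 8.3 prevails if the two sections ever disagree on treatment-emergent status.

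The cost is a line or two of SAP text and one condition in the AE date derivation. The protocol and data collection do not change.

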### **9.7.2 Laboratory Data**

Laboratory evaluations will be collected at Screening, Day 28, Day 56, Day 85/ETD, and Follow-Up (Day 113). All laboratory results including hematology, chemistry, endocrinology, reproductive endocrinology, urinalysis, and urine microscopic parameters will be listed (see Appendix D for the list of parameters for each category). The observed results and change from baseline for hematology, chemistry, endocrinology, and reproductive endocrinology will be summarized descriptively by visit and by treatment group. Baseline for laboratory tests is defined as the last assessment performed prior to Day 1 dosing date. Most subjects have Screening visit as baseline.

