1.3 Serlopitant

1.3.1 Serlopitant Background

Serlopitant is a small molecule, highly selective NK₁-R antagonist that is administered orally and metabolized by CYP3A4, with a plasma half-life of 45–86 hours. It binds with high affinity to the human NK₁-R with a dissociation constant (K_d) of 46 pM; displacing SP binding with a half-maximal inhibition concentration (IC₅₀) of 61 pM. Serlopitant is a potent functional antagonist of SP-induced inositol phosphate generation.

Serlopitant has been extensively studied in animal toxicology studies, including chronic toxicology and carcinogenicity studies. In non-clinical chronic toxicology studies in rats, mice and dogs, treatment related findings of potential clinical significance included increased salivation, decreased body weight gain and food consumption, slight changes in hematology and serum biochemistry parameters, mild increases in liver weight and mild histomorphologic changes. The histomorphologic changes were seen only in rats (not in dogs or mice) and included: very slight ovarian interstitial cell hypertrophy, mammary gland and uterine atrophy; decreased corpora lutea; increased histiocytes in lung and mesenteric lymph nodes; slight skeletal and cardiac muscle degeneration; slight increased hematopoiesis in bone marrow; and slight to moderate vacuolation in kidney tubules. These nonclinical findings occurred at systemic exposures exceeding those anticipated to provide efficacy of serlopitant for pruritus indications in humans (1 to 5 mg tablet daily). No cardiac lesions have been observed in dog toxicity studies up to 9 months in duration nor in a 3-month mouse range-finding study and 2-year mouse carcinogenicity study at exposure higher than the lowest level which caused cardiotoxicity in rats. The no observed adverse effect level (NOAEL) in rats for histomorphological changes in the reproductive tract, mammary gland and bone marrow provides a 2.5-fold margin for the maximum-targeted exposure (5 mg tablet daily). The rat NOAEL for histomorphological changes in muscle and kidney provides a 5-fold margin for the maximum-targeted exposure (5 mg tablet daily).

In summary, the nonclinical toxicity noted with serlopitant provides no contraindications to the continuation of clinical trials via the oral route. Findings in the developmental toxicity studies support inclusion of women of childbearing potential in clinical trials in accordance with the study protocol and local regulatory guidances.

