6.2.3 Clinical Laboratory Assessments

Samples for hematology, chemistry, urinalysis, and serum pregnancy testing (when necessary) will be collected as outlined in [Appendix A](#) and at unscheduled study visits when clinically indicated, and analyzed at a central laboratory unless otherwise specified. Detailed instructions regarding sample collection, preparation, and shipment can be found in the laboratory manual. Laboratory assessments will include the following:

- Hematology: hematocrit, hemoglobin, red blood cell count, red blood cell indices, platelets, white blood cell count, white blood cell differential (neutrophils, lymphocytes, monocytes, basophils, eosinophils)
- Chemistry: sodium, potassium, chloride, bicarbonate, glucose, blood urea nitrogen, creatinine, calcium, phosphorus, magnesium, albumin, ALT, AST, alkaline phosphatase, total bilirubin, LDH, uric acid, total protein, lipid panel
- Pregnancy testing: all females of childbearing potential will have a local urine pregnancy test performed. Positive or equivocal urine pregnancy test results will be confirmed by a serum pregnancy test analyzed at a central laboratory. A serum pregnancy test will be done at Screening.
- Urinalysis: color, clarity, pH, specific gravity, bilirubin, glucose, ketones, leukocytes, nitrite, blood, protein, urobilinogen, microscopic analysis
- Endocrine: TSH, free T4, cortisol, corticotropin
- Reproductive endocrinology (for all female subjects under 55 years of age at consent): serum FSH, LH, estradiol, progesterone, Anti-Mullerian hormone (AMH)

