Subjects with clinical laboratory values outside of the normal reference range at any post-baseline assessment will be summarized. Shifts from baseline laboratory values will be tabulated.

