#### **9.7.2.1 Abnormal Laboratory Results**

For each quantitative hematology, chemistry, endocrinology, and reproductive endocrinology (AMH test only) laboratory parameter, observed values will be compared to normal laboratory reference ranges and classified as “Low”(where applicable), “Normal”, “High (if applicable). For each laboratory parameter, a 4x4 contingency table (shift table) will be displayed that summarizes the counts of subjects who were classified as “Low”, “Normal”, “High” or result missing at Baseline vs. “Low”, “Normal”, “High” or result missing at Post-baseline time points, where Post-baseline time points are Day 28, Day 56, Day 85/ETD, and Day 113. Separate shift tables will be generated for each treatment group at each visit. A listing of abnormal laboratory results will be provided.

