**Urine Microscopic**

7BAC	BACTERIA(/HPF)
V7OXC	CA OXALASTE CRYSTALS (/HPF)
7EPIR	EPITHELIAL RENAL (/HPF)
7EPIS	EPITHELIAL SQUAMOUS (/HPF)
7EPIT	EPITHELIAL TRANSITIONAL (/HPF)
V7GRC	GRANULAR CAST (/LPF)
7UHC2	HYALINE CAST (/LPF)
V7RCS	RBC CAST (/LPF)
7URBC	RBCS (/HPF)
V7TPC	TRI PHOSPHATE CRYSTALS (/HPF)
V7UAC	URIC ACID CRYSTALS
V7WAC	WAXY CAST (/LPF)
V7WCS	WBC CAST (/LPF)
7UWBC	WBCS (/HPF)
V7YST	YEAST (/HPF)

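### The SAP sends urinalysis and urine microscopy to listings only, although the protocol promises out-of-range summaries and shift tables for laboratory values without excepting urine

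*SAP*

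**What the plan says.** **Collection.** Protocol 6.2.3 includes this panel among the laboratory assessments: "Urinalysis: color, clarity, pH, specific gravity, bilirubin, glucose, ketones, leukocytes, nitrite, blood, protein, urobilinogen, microscopic analysis". The protocol's schedule (Appendix A, Table 3) places urinalysis at Screening and at Days 28, 56, 85/ETD and 113. SAP Appendix D itemises the microscopy, including renal epithelial cells and granular, hyaline, waxy, RBC and WBC casts.

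**Protocol commitment.** Protocol 8.10.2 promises visit-wise summary statistics for laboratory results. It adds: "Subjects with clinical laboratory values outside of the normal reference range at any post-baseline assessment will be summarized". It then says that shifts from baseline will be tabulated. Urine is not excepted.

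**SAP output.** SAP 9.7.2 says that all results, urinalysis and urine microscopy included, will be listed. The summaries are narrower: "The observed results and change from baseline for hematology, chemistry, endocrinology, and reproductive endocrinology will be summarized descriptively by visit and by treatment group". The shift tables in SAP 9.7.2.1 are narrower still: "For each quantitative hematology, chemistry, endocrinology, and reproductive endocrinology (AMH test only) laboratory parameter, observed values will be compared to normal laboratory reference ranges". That section also provides a listing of abnormal results.

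**Nonclinical background.** Protocol 1.3.1 introduces its animal findings with "treatment related findings of potential clinical significance included increased salivation" and includes in the list "slight to moderate vacuolation in kidney tubules". It says that the histomorphologic changes occurred only in rats, and it gives the exposure margin: "The rat NOAEL for histomorphological changes in muscle and kidney provides a 5-fold margin for the maximum-targeted exposure".

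**The concern.** The SAP is the document that the programmers will follow. If it is followed as written, a difference between arms in urine protein, glucose, blood, tubular cells or casts would have to be found by reading subject-level listings. No laboratory table would give a count or percentage by arm. The study report could then describe the laboratory data as unremarkable without having compared the arms on urine.

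Two things make this worth raising. The protocol appears to promise such tables, and the SAP narrows that promise without giving a reason. The protocol's own animal data also include a kidney-tubule finding, and urinalysis is one of the panels bearing on the kidney.

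**Working it through.** The plan states no figure for this point, so the check is a comparison of texts.

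**1. What is listed and what is tabulated (SAP 9.7.2 and 9.7.2.1).**

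| Panel | Listed | By-visit, by-arm summary | Shift table |
|---|---|---|---|
| Hematology | yes | yes | yes (quantitative) |
| Chemistry | yes | yes | yes (quantitative) |
| Endocrinology | yes | yes | yes (quantitative) |
| Reproductive endocrinology | yes | yes | AMH only |
| Urinalysis | yes | no | no |
| Urine microscopy | yes | no | no |

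Six categories are listed and four are summarized. The two left out are urinalysis and urine microscopy, and neither returns in the shift tables.

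**2. Protocol 8.10.2 against the SAP, for urine.**
- Summary by visit: promised for laboratory results; the SAP gives none.
- Subjects out of range after baseline: summary promised; the SAP gives a listing of abnormal results.
- Shifts from baseline: tabulation promised; the SAP gives none.

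**3. Is there another route to a by-arm table?**
- Protocol 7.1.3 makes a post-dose laboratory abnormality an adverse event only if the investigator considers it clinically significant. SAP 9.7.1 tabulates treatment-emergent events by arm. This route exists, but it is filtered by judgement.
- SAP 8.1 says in general terms that categorical variables are summarized by counts and percentages. SAP 9.7.2 is the specific text, and it names the panels to be summarized. The general line does not clearly override it.
- No other SAP section tabulates urine results.

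**4. Are the data there?** There is a screening value, which SAP 9.7.2 says is the laboratory baseline for most subjects, and there are four post-baseline assessments. At full retention that is 170 × 4 = 680 post-baseline samples. Of these, 170 × 3 = 510 come from Days 28, 56 and 85/ETD and 170 from Day 113, after treatment. The plan expects 15% dropout. If those subjects supplied no post-baseline sample at all, the total would be 0.85 × 680 = 578. The range of 578 to 680 shows only that a table is feasible; it does not measure any lost signal.

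**5. Can the lost signal be sized?** No. The documents give no expected rate of abnormal urine findings in either arm, so any figure would be an assumption.

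**The case against.** The other side has several good arguments.

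- **The kidney finding is weak evidence of a human risk.** It is rat histology, seen at exposures above those expected to be effective, with a 5-fold margin. It is one item in a long list. The protocol concludes that the nonclinical toxicity does not preclude further trials, and it names no renal event of interest. This stands, and it keeps the point minor.
- **Renal chemistry is tabulated.** Creatinine, blood urea nitrogen, phosphorus, bicarbonate and uric acid are in the chemistry panel, which gets both summaries and shift tables. This stands. A reader might infer that urine is the most direct marker of tubular injury, or that injury would show in urine while serum chemistry stayed normal. The documents say neither, and the point does not need either.
- **The adverse-event tables are a partial safeguard.** A reader might infer that no table of any kind could show a difference. That is too strong: abnormalities judged clinically significant could appear there. The supportable statement is that no *laboratory* table would show one.
- **The protocol wording suits quantitative tests.** Protocol 8.10.2 does not name urinalysis, and color or clarity has no mean. The schedule also gives urinalysis its own row, apart from clinical laboratory sampling. So a plain breach of protocol is arguable. But Protocol 6.2.3 places urinalysis among the laboratory assessments, and out-of-range counts and category shifts suit categorical results. The data type explains a different format, not the absence of any table.
- **Abnormal results are listed, and a safety team reviews data.** Both are true. However, a listing gives no count by arm, and under Protocol 3.4.1 the team sees blinded data.

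**Conclusion.** The point holds as a minor discrepancy between protocol and SAP. Read naturally, the protocol promises out-of-range summaries and shift tables that cover urine. The SAP provides listings only, without explanation. The consequence is one missing by-arm safety comparison, with the adverse-event tables as a partial and judgement-dependent substitute.

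The conclusion rests on two readings: that Protocol 8.10.2 covers every panel named in Protocol 6.2.3, and that SAP 9.7.2 means what it says when it names four panels for summary. If Protocol 8.10.2 was meant for quantitative tests only, what remains is a gap in wording that the SAP should explain.

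A reader might infer that serlopitant has a known human renal risk that the SAP fails to examine. The documents do not support that: the finding is confined to rats, and serum renal chemistry is compared between arms. Efficacy, error rates and sample size are not affected, and no clinical management rule is involved.

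**What to change.** Bring SAP 9.7.2.1 into line with Protocol 8.10.2 by adding, by treatment group:

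1. A shift from baseline to worst post-baseline category for urine protein, glucose and blood. Use normal/abnormal, or the grades that the central laboratory reports. Those formats are not visible in the available text, so the SAP should name the ones actually supplied.
2. The number and percentage of subjects with newly abnormal renal epithelial cells, casts, RBC or WBC at any post-baseline assessment, with abnormal defined by the central laboratory's flag.

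Keep the existing listings. If the sponsor prefers not to tabulate urine, the SAP should say so and give the reason for departing from Protocol 8.10.2.

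The cost is SAP wording and one or two more descriptive tables from data already collected. No samples, visits or procedures are added. The tables are descriptive, so they should be read without formal testing.
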